- One surgeon perform all operation
- Local anaesthesia 2% lidocaine and ephinephrine 3x2 ml lidocaine
- Trapezoid submarginal flap (Ochsenbein-Luebke flap)
- 15 C surgical blade
- Ball shaped 0,27 mm diameter bone burr, 1:1 straight handpiece
- 3 mm of apical portion is resected- in one piece – perpendicular to the long axis placed in sterile saline
- 3 mm retrograde cavity- with diamond coated ultrasonic instruments
- Microbiological sample
- MTA retrograde RCFilling
- Mobilisation of the flap
- In the test group the resection cavity was filled and covered with A-PRF+ membrane
- Tension free flap closure with 3-0 Silc suture

PRF preparation

- In the test group before surgery 3 or 2 (depends on size of the cavity) 10ml glass tubes without additives
- 1300 rpm for 8 min centrifugation (Harmonycom)
- Using an A-PRF Duo centrifuge (Process for PRF, Nice, France)
- Placed in sterile container (PRF Box, Process for PRF, Nice, France)

Postoperative instruction

- Diclofecan 50mg (Cataflam 50mg) 2x1 per day, for 3 days
- Rinses with 0,12% Chlorehexidine twice a day for 1 week
- No postoperative antibiotics was described
- Suture removal after 7 days

Evaluation

- 3D optical scans (Einstar, Shining 3D) were recorded over two time period, T0 (preoperative scan), T1 (day 3 postoperatively)
- VAS (Visula Analogue Scale) pain was graded on a score to 0-10, 0 no pain, 10 maximum intensity of pain, for 7 days
- Likert scale based questionnaire: ranging from 0 to 4, 0 non 4 very much, for 7 days daily starts on the operation day
 - Postoperative limitations in function: Mouth opening, Chewing, Speaking, Sleeping, Daily routine, Work

Statistical Analisys

Statistical Analysis Plan

1. Study Objectives

- **Primary Objective:**
 - To assess the impact of PRF membrane on postoperative swelling and its relationship with quality of life dimensions and pain.
- **Secondary Objectives:**
 - To compare quality of life (QoL) dimensions and pain levels pre- and post-intervention between the PRF membrane group and the control group.
 - To investigate correlations between swelling (volume) and postoperative QoL dimensions.

2. Study Design

- **Type:** Preliminary comparative study.
- **Groups:**
 - **PRF Membrane Group** (10 participants): Underwent apicoectomy with PRF membrane application.
 - **Control Group** (10 participants): Underwent apicoectomy without PRF membrane.

3. Outcome Measures

1. **Primary Outcomes:**

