 - Postoperative swelling (volume): Measured using standardized evaluation methods.
 - Quality of Life (QoL) dimensions: Assessed using a questionnaire with subdimensions (e.g., physical function, pain impact, anxiety, sleep disturbance).
2. **Secondary Outcomes:**
 - Pain intensity: Measured using the Visual Analog Scale (VAS).
 - Correlations between swelling and QoL dimensions.

4. Statistical Methods

1. **Descriptive Statistics:**
 - Mean \pm standard deviation for continuous variables (e.g., QoL scores, pain, swelling volume).
 - Frequency and percentage for categorical variables.
2. **Normality Testing:**
 - **Shapiro-Wilk test:** Conducted for each variable to determine whether parametric or non-parametric tests will be used.
3. **Comparative Analyses:**

- **Between Groups:**
 - Independent samples t-test for normally distributed data.
 - Mann-Whitney U test for non-normally distributed data.
- **Within Groups:**
 - Paired t-test for normally distributed pre- and post-intervention comparisons.
 - Wilcoxon signed-rank test for non-normally distributed data.

4. **Correlations:**

- Spearman's or Pearson's correlation will be used to evaluate the relationship between swelling (volume) and QoL dimensions depending on data distribution.

5. **Significance Threshold:**

- A two-tailed **p-value < 0.05** will be considered statistically significant.

5. Missing Data

- Missing data will be handled by:
 - **Listwise deletion** for analyses where missing data is minimal.
 - Sensitivity analysis if missing data exceeds 10%.

6. Software

- All statistical analyses will be performed using **SPSS** or **R** software.

7. Reporting

- Results will include:
 - Comparative tables of pre- and post-intervention outcomes.
 - Statistical significance levels for group comparisons.
 - Correlation matrices for swelling and QoL dimensions.

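### SAP section 3 makes QoL dimensions primary while section 1 makes the QoL group comparison secondary; no QoL summary, day or success rule is named, and p < 0.05 is the only threshold

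*Combined protocol and SAP*

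**What the plan says.** **Roles of the outcomes.** SAP section 3 lists two primary outcomes. One is swelling volume. The other is "Quality of Life (QoL) dimensions: Assessed using a questionnaire with subdimensions (e.g., physical function, pain impact, anxiety, sleep disturbance", where the list is given as examples. SAP section 1 has the primary objective "To assess the impact of PRF membrane on postoperative swelling and its relationship with quality of life dimensions and pain" and, among the secondary objectives, "To compare quality of life (QoL) dimensions and pain levels pre- and post-intervention between the PRF membrane group and the control group". Section 1 also makes the swelling-QoL correlations a secondary objective, and section 3 makes "Correlations between swelling and QoL dimensions" a secondary outcome.

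**What is collected.** The Evaluation section describes a "Likert scale based questionnaire: ranging from 0 to 4, 0 non 4 very much, for 7 days daily starts on the operation day", with the items "Postoperative limitations in function: Mouth opening, Chewing, Speaking, Sleeping, Daily routine, Work". Swelling has one preoperative scan and one scan on day 3. Pain is a 0-10 VAS for 7 days.

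**How it is tested.** SAP section 4 offers a t-test or Mann-Whitney test between groups, paired tests within groups, and correlations of swelling with QoL dimensions. The one decision threshold is "A two-tailed p-value < 0.05 will be considered statistically significant". Section 7 promises "Comparative tables of pre- and post-intervention outcomes".

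SAP section 2 calls the study preliminary, with 10 patients per group.

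**The concern.** Each between-group test needs one value per patient, and for QoL the plan does not say which value. It names no total score, item, day or average. Two current sections also disagree on whether the QoL group comparison is primary. The swelling-QoL relationship has the same problem: it is in the primary objective, but also a secondary objective and a secondary outcome.

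Two things are at stake. First, the QoL result and its rank can be settled after the data are seen, so a chance difference on one item could be presented as a PRF benefit on a primary outcome. Second, if any one significant primary result is taken as success, the 5% threshold no longer describes the risk of a false claim.

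**Working it through.** **Inputs.** From the documents: 10 per group; two-sided 0.05; six QoL items; 7 days; one post-operative swelling scan. The documents give no correlations, score distributions or SDs, so those below are assumptions.

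**Step 1: the definitions side by side.** Of section 3's examples, sleep disturbance has a counterpart among the six Evaluation items. Pain impact and anxiety have none, and physical function is not an item. The items are headed as post-operative limitations, and section 1 also speaks of post-operative QoL, so the seven daily scores are most naturally all post-operative. No baseline QoL score is then described for the pre/post comparison that sections 1 and 7 plan.

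**Step 2: the plan's own figure.** With one deciding test, the error is 1 - 0.95^1 = 0.05. The stated threshold gives 5% only in that case.

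**Step 3: number of primary tests, k.**
- Swelling plus one QoL score: k = 2.
- Swelling plus one value per item: k = 1 + 6 = 7.
- Swelling plus every item on every day: k = 1 + 6 x 7 = 43.

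**Step 4: chance of at least one p < 0.05 with no PRF effect.** For independent tests this is 1 - 0.95^k. For correlated tests I used simulation: 10 v 10, 10,000 replicates per setting, 0-4 items and normal swelling. Assumed latent correlations were 0.3-0.9 between items and 0.5-0.95 within an item over days. The swelling loading was 0.3 or 0.7, and there were three assumed score distributions.

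| k | Independent | Correlated, t-test |
|---|---|---|
| 2 | 1 - 0.95^2 = 0.098 | 0.080-0.102 |
| 7 | 1 - 0.95^7 = 0.302 | 0.104-0.286 |
| 43 | 1 - 0.95^43 = 0.890 | 0.249-0.847 |

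Mann-Whitney results were similar. For k = 2, two normal outcomes with correlation 0 to 0.9 (200,000 replicates) gave 0.098 down to 0.071, so I quote 0.07-0.10. Simulated values above 0.098 are approximation and simulation noise. Swelling alone came out at 0.043-0.057 across settings, so the simulated ranges are good to roughly 0.01.

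**Step 5: if swelling and one QoL score must both be significant.** Independent: 0.05 x 0.05 = 0.0025. At correlation 0.9: 0.028. Both are below 0.05.

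**Step 6: after the fix.** Swelling is tested once, so its error is 0.05. Holm across six item summaries gave a simulated QoL error of 0.011-0.057; the excess over 0.05 is no larger than that seen for swelling alone. The first Holm step is 0.05/6 = 0.0083. From the noncentral t distribution (n = 10 per group, 18 df, noncentrality d x sqrt(10/2)), the effect detectable with 80% power is:
- 1.32 SD at 0.05;
- 1.48 SD at 0.025;
- 1.73 SD at 0.0083.

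**Step 7: why the summary must be fixed in advance.** Assume normal scores, equal day-to-day correlation r, and a 1.5 SD effect on three early days only. A 7-day mean has standardised effect (1.5 x 3/7)/sqrt((1 + 6r)/7). A 3-day mean has 1.5/sqrt((1 + 2r)/3). For r = 0.5 these are 0.85 and 1.84; for r = 0.9 they are 0.67 and 1.55. Over that range of r, power at 0.0083 is 0.10-0.18 for the 7-day mean and 0.69-0.86 for the 3-day mean. These figures do not carry over directly to skewed 0-4 scores.

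**The case against.** **The study is preliminary.** With 20 patients and no stated success claim, strict family-wise control is not clearly required. This stands as a reason to lower the severity. It does not remove the point, because the SAP still names primary outcomes, sets a significance threshold and plans to report significance for group comparisons.

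**No adjustment is only silence.** True: the SAP never says the tests are unadjusted. It gives one threshold and mentions no correction, hierarchy or success rule.

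**Stronger readings that the documents do not support.**
- A reader might infer that a false-positive primary result is nearly certain, at 0.89. That needs all 43 tests to be run as primary and to be independent. The plan states no such testing, and repeated items in the same patients will be correlated.
- A reader might infer that one significant result is the plan's success rule. The plan states no rule. Requiring both outcomes would give no inflation.
- A reader might take the operation-day score as a baseline. The heading over the items points the other way. The real gap is that no baseline QoL score is described.
- A reader might infer that the swelling-pain relationship has no analysis at all. Pain impact is among section 3's example dimensions, so the QoL correlations could partly cover it. What is missing is swelling with VAS.

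**Swelling as sole primary is a judgement.** The Aim lists swelling, QoL and pain together. This stands, so the fix includes an alternative that keeps QoL primary.

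**Conclusion.** The conflict between sections 1 and 3, and the absence of a QoL summary, day and success rule, are plain on the page and need no assumption. Under every reading, the QoL result can be chosen after the data are seen.

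The error rates are conditional. If any one significant primary result counts, they are about 0.07-0.10 for two tests and about 0.10-0.29 for seven. They are about 0.25-0.85 for 43 tests, a reading the plan permits but does not state. They rest on assumed correlations and score distributions and should be read as illustrative. If swelling and one QoL score must both be significant, the error is about 0.002-0.03 and there is no inflation.

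This should be fixed before analysis. Because the study is preliminary, it is not a fatal fault.

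**What to change.** **Main change.** Reconcile SAP sections 1 and 3. Make day-3 swelling volume change (T1 minus T0) the single primary outcome, tested once at two-sided 0.05. Keep the between-group QoL comparison secondary, as section 1 has it.

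**QoL.**
- State that the six Evaluation items are the QoL dimensions.
- Fix one post-operative summary per item before analysis, choosing the days by when an effect is expected (for example, the mean of the daily scores).
- Test each item once with Holm across the six, or label the QoL tests exploratory.
- Confirm that the operation-day score is post-operative. Drop the pre/post QoL comparison if there is no baseline score.

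**Other analyses.** Use one summary for VAS. Label the VAS, within-group and correlation p-values exploratory. Name the QoL and pain value to be correlated with day-3 swelling, and add swelling-VAS to the correlation method in section 4.

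**Alternative.** If QoL is to stay primary, name one QoL summary and apply Holm across it and swelling.

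**Cost.** The change is wording only, with no new patients or data. QoL loses primary status. At the first Holm step the effect detectable with 80% power rises from about 1.32 to 1.73 SD, or to 1.48 SD under the alternative. Parts of the text are in the past tense; if outcome data have already been seen, rewording cannot restore prespecification and the change must be reported as post hoc.
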